10.4.2. Secondary and safety outcomes

The secondary outcomes related to the primary PSA, UA/UC, and DM outcomes included:

- PSA
 - Prostate biopsy in older men
 - Prostate MRI in older men
 - New prostate cancer diagnosis in older men

- UA/UC
 - Total urinalysis use in women aged 65 and older
 - Total urine culture use in women age 65 and older
 - Antibiotic treatment in women age 65 and older (all oral UTI treatments)
 - Antibiotic treatment in women age 65 and older (nitrofurantoin and Fosfomycin only)
 - C. difficile infection in women age 65 and older
 - Rash in women age 65 and older
- DM
 - Hypoglycemia requiring an urgent care visit (not emergency department) among eligible patients

We will also measure the three co-primary outcomes monthly during a follow-up period (months 19-30) to evaluate the persistence of any effects observed during the study period.

We did not study any safety endpoints related to the PSA primary outcome. The safety endpoints related to the UA/UC and DM primary outcomes were deemed serious adverse events, and included:

- EHR-identified ED or hospital care possibly due to UTI or sepsis among women 65 and over following an office visit
- EHR-Identified ED or hospital care possibly due to hyperglycemia among previously tightly controlled
- Poor diabetes control ($\text{HbA1c} > 9\%$) among individuals who were previously tightly controlled ($\text{HbA1c} < 7\%$)

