4.2 Patient eligibility

All patients aged 65 years and older will be included in the overall study patient population. We will assess study outcomes for all clinics, clinicians and individual patients who meet the pre-defined study eligibility criteria for each measure.

Co-Primary Outcome	Eligibility Criteria
PSA	All adult men aged 76 years and older with a visit to a participating primary care or geriatrics NM clinic between September 1, 2018 – February 28, 2023
DM	All adults aged \geq 75 years old with a visit to a participating primary care or geriatrics NM clinic visit between September 1, 2018 – February 28, 2023
UA/UC	All adult women aged 65 years and older with at least one primary care, geriatrics, or immediate care NM visit between September 1, 2018 – February 28, 2023

Note: all subjects over the age of 89 years will be aggregated into a single category. We will obtain these outcomes by queries of the NMEDW. Some data are prospective in that they do not exist at the time of

IRB submission but retrospective in that we will only have access to them after collected in NM Epic as part of routine care delivery.

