DM. Diabetes Overtreatment in the Elderly (DM) is defined as the having the most recent hemoglobin A1C during the measurement period or during the year prior to the measurement period (if no A1C obtained during the measurement period) of less than 7.0 among adults aged 75 years and older with a diagnosis of diabetes mellitus who have insulin or an oral hypoglycemic (e.g., sulfonylurea or meglitinide, Protocol Supplement 4, pg. 12) on their active medication list at the end of the study period. Patients are attributed to the primary care clinician with whom they had the greatest number of visits during the measurement period. The measurement period is the 365 days preceding the measurement date.

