8. SAFETY ASSESSMENTS

We did not study any safety endpoints related to the PSA primary outcome. The safety endpoints related to the UA/UC and DM primary outcomes were deemed serious adverse events, and included:

- EHR-identified ED or hospital care possibly due to UTI or sepsis among women 65 and over following an office visit
- EHR-Identified ED or hospital care possibly due to hyperglycemia among previously tightly controlled
- Poor diabetes control ($\text{HbA1c} > 9\%$) among individuals who were previously tightly controlled ($\text{HbA1c} < 7\%$)

The Principal Investigator will report any unanticipated events to the IRB as well as the Data Safety and Monitoring Board (DSMB) assembled for this study. When notified of an unanticipated event, the DSMB will convene and make a decision as to whether the study should continue. The IRB will also be notified of the DSMB's decision.

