10.4 Outcomes

10.4.1 Co-primary outcomes

This study has 3 co-primary outcomes, referred to as PSA, UA/UC, and DM (defined in Section 6 above). They capture the over-testing, over-screening, and over-treatment of older patients, who may need less care than they are receiving. The ICD-10 codes used to capture these co-primary outcomes are defined in detail in the Supplement to this document. These outcomes are computable clinical quality measures that are abstracted from the EHR. They were previously validated as part of pilot work for this study. These will be extracted from the EHR on a monthly basis, with data for each month representing a 365 look-back period.

An office visit will be eligible for inclusion in the outcome denominator if it meets the following criteria:

PSA. Men were eligible for the PSA over-screening measure if they were age 76 years or older and attended at least one visit in the 365 days prior to the measurement date (for example, 365 days prior to February 1, 2020) with a clinician included in the study. Eligible patients had no history of prostate cancer (determined via diagnosis or procedure code) and were not taking an androgenic agent or anabolic steroid as of the measurement date.

UA/UC. Women were eligible for the urine testing for non-specific reasons (UA/UC) measure if they were age 65 years or older and had an in-person ambulatory care visit with a participating clinician in the 365 days prior to the measurement date where a urinalysis and/or urine culture was obtained in the interval 24 hours before to 48 hours after the visit. If a woman had multiple qualifying visits in the 365-day window, only the first was included.

DM. Patients were eligible for the diabetes over-treatment measure if they were age 75 years or older with a diagnosis of diabetes mellitus and their most recent hemoglobin A1C in the 365 days prior to the measurement date was less than 7.0%. Patients were attributed to the primary care clinician with whom they had the greatest number of visits in the 365-day window.

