10.5 Statistical Analyses

We will use the following descriptive statistics to characterize the sample: Means and medians for continuous measures, frequencies for count data, standard deviations and interquartile ranges for variance.

To test our 3 co-primary hypotheses, we will employ a mixed-effects hierarchical logistic regression model to estimate the adjusted marginal effect over time of each intervention on the 3 co-primary outcomes. Fixed effects will include intervention assignment, time period (historical baseline versus intervention period), time period interacted with intervention assignment, time (continuous, linear), and a 3-way interaction term between time period, intervention, and time (continuous). The coefficient on the 3-way interaction term will represent whether the log-odds of the monthly rate of change in each co-primary outcome differs between intervention and control patients during the intervention period. Providers will be included as random effects. To isolate the effect of the intervention on the co-primary outcomes, we will also include fixed effects for the variables included in the constrained randomization procedure.

The secondary and safety outcomes will be examined in a similar fashion. If they are sufficiently rare (for example, no events in a given month), model convergence may become an issue. First, we plan to expand the time frame from months to quarters and fit the same model. If that fails, we will abandon the time-varying aspect of the analysis and do one pull for the historical baseline period and one pull for the intervention period. The mixed effects logistic regression model would then be run without including continuous time. If that still fails to converge, we will exclude the random effects for providers and use a fixed effects logistic regression model.

Last, the three co-primary outcomes of interest will be examined in the following pre-specified subgroups:

- Sex (DM measures only)
- Race and ethnicity
- Age groups (for UA/UC: 65-74, 75-84, 85+) (for PSA: 76-79, 80-84, 85+) (for DM: 75-79, 80-84, 85+). We will also examine for effects on patients younger than the target populations (for UA/UC: 50-64, PSA: 70-75, DM 65-74).

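### The hypoglycemia outcome is restricted to eligible patients with no time anchor; on the natural reading, its denominator depends on A1C or drug status after randomisation, which the nudge is meant to change

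*Combined protocol and SAP*

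**What the plan says.** Sections 6.2 and 10.4.2 list one secondary outcome for diabetes: "Hypoglycemia requiring an urgent care visit (not emergency department) among eligible patients". Neither says which definition of eligibility applies or when it is assessed. Three definitions are available:

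- **4.2:** adults aged 75 or older "with a visit to a participating primary care or geriatrics NM clinic visit between September 1, 2018" and February 28, 2023. There is no diabetes, A1C or drug criterion.
- **6.1:** adults aged 75 or older with diabetes and with insulin or an oral hypoglycemic "on their active medication list at the end of the study period". Here an A1C below 7.0 is the event.
- **10.4.1:** "Patients were eligible for the diabetes over-treatment measure if they were age 75 years or older", had a diabetes diagnosis, and their "most recent hemoglobin A1C in the 365 days prior to the measurement date was less than 7.0"%. Here the A1C is part of the denominator and no drug is required.

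Section 10.4.1 has the co-primary measures extracted monthly, "with data for each month representing a 365 look-back period". Section 10.5 then states: "The secondary and safety outcomes will be examined in a similar fashion". If events are rare, 10.5 moves to quarters and then to one data pull per period, without saying how eligibility is set there.

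The two diabetes safety outcomes refer instead to earlier status, for example "EHR-Identified ED or hospital care possibly due to hyperglycemia among previously tightly controlled".

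**The concern.** The diabetes alert encourages the clinician to reduce medication (5.1). Under 6.1 or 10.4.1, that action, or the A1C that follows it, can decide whether the patient is still counted. A denominator formed this way selects on a response that only one arm is prompted to make. Randomisation no longer protects the comparison, although 10.1 describes the framework as intention-to-treat.

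The look-back adds to this. Status at the end of the window decides whether events earlier in the window count. Suppose a patient has hypoglycemia in month 2. If the drug is later stopped (6.1), or the A1C later reaches 7.0 or more (10.4.1), that patient leaves the denominator and the event goes too. A single pull for the whole intervention period would not cure this if eligibility were set at its end.

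Hypoglycemia is a reason for leniency that clinicians themselves gave in the interviews reported in 2.2. It is also the only diabetes outcome, apart from the co-primary process measure, on which a benefit could show. If it is measured in one population and hyperglycemia in another, benefit and harm cannot be set side by side.

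**Working it through.** The plan gives no rate, effect size or power for hypoglycemia, so there is no figure to reproduce. The check has two parts.

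**1. Who leaves the denominator when treatment is reduced?**

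| Definition | Leaves | Stays |
|---|---|---|
| 10.4.1 | Latest A1C now 7.0 or more, or no A1C in the 365 days | Drug reduced or stopped, latest A1C still below 7.0 |
| 6.1 | No listed drug remains active | Dose reduced, or one drug of several stopped, whatever the A1C |
| 4.2 | Nobody, on drug or A1C grounds | All |

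So a reduction does not by itself end eligibility. Under the two detailed definitions, some reduced patients leave and some stay.

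**2. What could this do to the comparison?** Set the hypoglycemia risk of patients whose treatment is not reduced to 1. Inputs:

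- f = 0.34, the share with therapy reduced. This is the pilot figure in 2.2. It measures reduction, not loss of eligibility, and is borrowed only for illustration.
- q = share of reduced patients who leave the denominator (assumed, 0 to 1).
- RR = effect of reduction on hypoglycemia risk (assumed, 0.25 to 0.75).
- k = baseline risk of reduced patients relative to the others (assumed, 0.5 to 3).
- No reduction in the control arm (assumed).

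Formulas, intervention over control:

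- Control level: C = (1 − f) + f·k
- Fixed cohort: [(1 − f) + f·k·RR] / C
- Rolling denominator: {[(1 − f) + f(1 − q)·k·RR] / [(1 − f) + f(1 − q)]} / C

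With k = 1 and RR = 0.5, C = 0.66 + 0.34 = 1:

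- Fixed cohort: 0.66 + 0.17 = 0.83
- Rolling, q = 0.5: (0.66 + 0.085) / (0.66 + 0.17) = 0.745 / 0.83 = 0.898
- Rolling, q = 1: 0.66 / 0.66 = 1.00

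Varying k, with RR = 0.5:

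| k | Fixed cohort | Rolling, q = 0.5 | Rolling, q = 1 | Effect of rolling |
|---|---|---|---|---|
| 0.5 | 0.898 | 1.020 | 1.205 | Reversed |
| 1 | 0.830 | 0.898 | 1.000 | Diluted, then hidden |
| 2 | 0.746 | 0.746 | 0.746 | None |
| 3 | 0.696 | 0.656 | 0.595 | Exaggerated |

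Varying RR at k = 1 and q = 0.5: true ratios of 0.745, 0.830 and 0.915 (RR 0.25, 0.5, 0.75) are seen as 0.846, 0.898 and 0.949.

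The direction depends on k·RR, the risk of reduced patients after reduction relative to the others. Below 1, their departure raises the intervention-arm rate; above 1, it lowers it; at exactly 1 (k = 2, RR = 0.5) it changes nothing.

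**The case against.** The strongest reply is that the text says only that patients are eligible. Monthly reassessment is stated for the co-primary outcomes, and the sentence in 10.5 that extends the approach to secondary outcomes follows a description of the regression model, not of denominators. That is correct: reassessed eligibility is an inference. It is still the natural one, because the only two detailed definitions use status at the measurement date or at period end, and no pre-activation anchor appears anywhere. The 4.2 row would avoid the problem, but it does not require diabetes and is an unlikely denominator for this outcome.

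A reader might go further and infer that the expected benefit cannot appear, because everyone whose treatment is reduced drops out. The documents do not support that. Many reduced patients would stay under either detailed definition, and at equal baseline risk the benefit vanishes only if all of them leave. Nor can the pilot's 34% be read as the share lost or as the size of a hidden effect.

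Three further points stand:

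- This is one of ten secondary endpoints, chosen according to 6.2 to identify other burdens on the healthcare system, and no power is claimed for it.
- The safety outcomes' reference to previous tight control also lacks a date, so those outcomes are not shown to use a pre-activation cohort.
- A historical comparison cohort is not trivial to build. Six practices have data only from June 1, 2019 (10.2), the periods last 12 and 18 months, and the pandemic gap lies between them (5.3).

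These limit the claim and shape the remedy; they do not remove the defect.

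**Conclusion.** The concern holds in a limited form. The hypoglycemia denominator has no stated definition or time anchor, and following either detailed DM definition makes it depend on post-randomisation status that the intervention is meant to change. This is more than missing detail, since applying the plan as written would most naturally produce response-dependent selection.

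Neither the size nor the direction of the bias can be determined from the documents. The calculated ratios rest on assumed values of q, RR and k and on the borrowed pilot share. They show that the error can go either way, not how large it will be. The argument affects the interpretation of this secondary outcome and its comparison with the diabetes safety outcomes. It does not by itself alter the co-primary DM test.

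**What to change.** 1. Reconcile the DM definitions in 4.2, 6.1 and 10.4.1, and state in 6.2 and 10.4.2 which one defines eligibility for hypoglycemia.
2. Analyse hypoglycemia in patients who meet that definition at the last measurement date before activation, kept in the denominator whatever their later drug or A1C status. By the look-back rule in 5.3, the 12 months before September 1, 2020 are March 1, 2019 to February 29, 2020.
3. Build the historical cohort by the same rule at the start of the historical period. State how the six later-acquired practices are handled and how 12 and 18 months of follow-up are made comparable, for example by rates per person-month. A simpler alternative is to compare arms within the intervention period, adjusting for baseline.
4. Anchor previous tight control to the same date for hyperglycemia care and A1C above 9%, so that benefit and harm share one cohort.
5. Report the rolling denominator as a sensitivity analysis, and say how eligibility is set if the one-pull fallback is used.

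The cost is SAP wording and a cohort flag built from EHR data. The intervention cohort needs nothing beyond data the trial already extracts. The historical cohort may need an earlier pull: 4.2 starts visits at September 1, 2018, only six months before March 1, 2019, whereas the look-back is 365 days. The downside is that patients first eligible after activation are shown only descriptively for this outcome.

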10.5 Statistical Analyses

We will use the following descriptive statistics to characterize the sample: Means and medians for continuous measures, frequencies for count data, standard deviations and interquartile ranges for variance.

To test our 3 co-primary hypotheses, we will employ a mixed-effects hierarchical logistic regression model to estimate the adjusted marginal effect over time of each intervention on the 3 co-primary outcomes. Fixed effects will include intervention assignment, time period (historical baseline versus intervention period), time period interacted with intervention assignment, time (continuous, linear), and a 3-way interaction term between time period, intervention, and time (continuous). The coefficient on the 3-way interaction term will represent whether the log-odds of the monthly rate of change in each co-primary outcome differs between intervention and control patients during the intervention period. Providers will be included as random effects. To isolate the effect of the intervention on the co-primary outcomes, we will also include fixed effects for the variables included in the constrained randomization procedure.

The secondary and safety outcomes will be examined in a similar fashion. If they are sufficiently rare (for example, no events in a given month), model convergence may become an issue. First, we plan to expand the time frame from months to quarters and fit the same model. If that fails, we will abandon the time-varying aspect of the analysis and do one pull for the historical baseline period and one pull for the intervention period. The mixed effects logistic regression model would then be run without including continuous time. If that still fails to converge, we will exclude the random effects for providers and use a fixed effects logistic regression model.

Last, the three co-primary outcomes of interest will be examined in the following pre-specified subgroups:

- Sex (DM measures only)
- Race and ethnicity
- Age groups (for UA/UC: 65-74, 75-84, 85+) (for PSA: 76-79, 80-84, 85+) (for DM: 75-79, 80-84, 85+). We will also examine for effects on patients younger than the target populations (for UA/UC: 50-64, PSA: 70-75, DM 65-74).

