5.3 Interruption due to COVID-19 Pandemic

The intervention period for BEAGLE was originally slated to begin in April 2020. However, on March 21, 2020, the governor of Illinois and mayor of Chicago issued a “stay-at-home” order to mitigate harm from the COVID-19 pandemic. This severely impacted regular primary care activities at Northwestern Medicine. As such, we chose to delay the start of the intervention until regular care resumed. The intervention was rolled out on September 1, 2020, and the look-back period for the study measures was adjusted to exclude data collected between March 1, 2020 and August 31, 2020. So, for example, study outcomes reported in December 2020 included the following 12 months of data: June 1, 2019 – February 29, 2020 plus September 1, 2020 – November 30, 2020.

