7. STUDY PROCEDURES

7.1 Schedule of Evaluations

Assessments	Historical practice: Baseline overuse (Month - 17 to Month 0)	Baseline, Enrollment, Randomization (Month 0, Day 1)	Intervention Start (Month 1)	Monitored and Measured Monthly	Intervention End (Month 18)	Follow-up Period (Month 19 to Month 30)
Clinician-level Assessments						
Informed Consent		X				
Demographics		X				
Inclusion/Exclusion	X					
Provider Attitudes Survey		X			X	
Patient-level Assessments						
ICD-10 codes	X	X	X	X	X	X
Ordering	X	X	X	X	X	X
Adverse Events	X		X	X	X	

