7.2 Description of Evaluations

7.2.1 Consent. We will send providers at participating sites an introductory email that includes a description of the broad goals of the study, a general description of the intervention, and a link to the electronic consent form and baseline survey. The consent document will indicate that participation is voluntary and that decisions to participate (or not) will have no bearing on any provider's status at his or her clinic. Providers who provide consent to participate will be asked to complete an online survey and brief educational session prior to the intervention phase, permit de-identified patient records pertaining to eligible patients who saw them to be included in the study database, and complete a 15-minute post-intervention survey. We will also describe compensation that providers will receive for participation.

7.2.2 Enrollment. The enrollment date will be documented on the online consent form at the time of consent. The interventions will be activated after all clinicians have been enrolled or declined to participate.

7.2.3. Baseline assessments. We will collect information about the rates of each of the 3 co-primary outcomes monthly for the 12 months leading up to the activation of the intervention. This period will document historical practice. We will also administer a survey to assess provider characteristics and provider attitudes toward practice guidelines, clinical decision support, and practice environment.

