10. STATISTICAL CONSIDERATIONS

10.1 General Design Overview

Hypotheses

Our primary hypothesis is that practices randomized to receive behavioral economic interventions will have decreases over time in the over-screening, over-treatment, and over-testing of older patients who

may no longer warrant such care. This hypothesis will be evaluated in an intention-to-treat difference-in-differences framework using a mixed-effects logistic regression model. Fixed effects will include the effects of interventions over time (i.e., interactions between randomization assignment and time), using a historical period 12 months prior to the intervention period. Providers and randomization unit (clinic) will be modeled as random effects.

Design

We will conduct a cluster randomized trial using data abstracted from the EHR at one academic health system. We chose a cluster-randomized design at the clinic level to minimize spillover effects – contamination that might occur if individual providers in close proximity are randomized to different interventions. The study design for BEAGLE included the implementation of a modified constrained randomization scheme, to ensure that clinics in each study arm were similar prior to activation of the intervention.

Outcome measures

This study has 3 co-primary outcomes, referred to as PSA, UA/UC, and DM (defined in Section 6 above, and further detailed in Section 10.4 below). They capture the over-testing, over-screening, and over-treatment of older patients, whose medical needs may have evolved to require less care.

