We used the methodology presented in [cite] to implement the constrained randomization algorithm. First, the study biostatistician ([name]) generated possible 1:1 randomization schemes. Since there were infinitely many ways to randomize the 60 practices into 2 groups, the study biostatistician decided to create 100,000 possible sequences. Second, the balance of the eight prespecified variables (which were “constrained” upon) was then evaluated in the 100,000 possibilities. Schemes were deemed candidate schemes if they had “adequate balance” – that is, the measure of imbalance for each variable (separately) could not surpass a pre-specified threshold. For categorical variables, we allowed no more than a difference of two practices across each arm. For continuous variables, we compared sample means across study arm, and adapted the ideas of the minimal sufficient balance approach. We called a variable ‘adequately balanced’ if a T-statistic from an independent two sample t-test with equal variance was between -0.385 and 0.385, corresponding to a p-value for the individual variable of 0.30. Last, the final sequence was selected from the candidate schemes (which were adequately balanced) at random with equal probability.

As was disclosed in the study protocol paper, we achieved adequate balance for seven of the eight pre-specified variables used in the constrained randomization algorithm. Due to a coding error, we applied balancing criteria for the PSA measure on the number of eligible patients (denominator) and the number of PSA orders (numerator) rather than the annual PSA overtesting rate (#4 above). This is an absolute measure instead of a relative measure that accounts for the size of the eligible patient population at each clinic. For a complete discussion of the implications of this error, please reference the protocol paper.

The study biostatistician ([name]) generated the final randomization in R version 3.6.4 (R Core Team, 2020). [25] Randomization occurred in June 2020. The allocation of the sequence was concealed until

after the intervention period began in September 2020 (due to interruption of regular care during the COVID-19 pandemic).

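### The primary model in Section 10.5 lists no period-by-time term and no time coding, so its three-way coefficient need not be the between-arm contrast it is said to be

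*Combined protocol and SAP*

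**What the plan says.** Section 10.5 tests each co-primary outcome with a mixed-effects logistic model. Its fixed effects are intervention assignment, period (baseline or intervention), "time period interacted with intervention assignment, time (continuous, linear), and a 3-way interaction term between time period, intervention, and time (continuous"), and the constrained-randomization variables. It says the three-way coefficient shows whether the monthly rate of change "differs between intervention and control patients during the intervention period".

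Four other places bear on this:

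- **Section 10.1** promises a difference-in-differences analysis and says: "Fixed effects will include the effects of interventions over time (i.e., interactions between randomization assignment and time"). Section 10.5 lists no two-way intervention-by-time term.
- **Section 7.2.3** collects "rates of each of the 3 co-primary outcomes monthly for the 12 months leading up to the activation of the intervention", so there are monthly baseline points to which a slope can be fitted.
- **Section 10.4.1** extracts outcomes monthly, "with data for each month representing a 365 look-back period".
- **Section 5.3** says that "the look-back period for the study measures was adjusted to exclude data collected between March 1, 2020 and August 31, 2020". Its example, the December 2020 report, combines nine pre-pandemic months with three new ones.

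Period by time is listed nowhere. No section says whether time runs through both periods, restarts, or is held at zero until the intervention starts.

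**The concern.** The concurrent control arm is there so that a trend common to both arms drops out of the comparison. For the three-way coefficient to do this, the control arm needs its own slope in the intervention period. If time runs through baseline, the listed terms do not provide one.

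A change in the common slope is plausible here. The two periods lie on either side of the excluded pandemic months. For a measure that accumulates over a 365-day look-back, a common shift in practice enters month by month and appears as a 12-month ramp. A shared fall would then exaggerate the apparent nudge effect, and a shared rise would partly hide it. The coefficient is the declared test for all three co-primary outcomes.

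**Working it through.** **Inputs.** Terms from Section 10.5; 12 baseline and 18 intervention months from the Précis; a 4.5-point reduction from 25% from Table 1 (PSA). Assumptions: 0/1 indicators, equal numbers per arm-month, and the sizes of the shared change. Random effects and randomization covariates are left out, since the question concerns the time, period and arm columns. The plan gives no figure of its own to reproduce.

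**1. Slopes implied by the listed terms.** Let A be arm, P period and T time:

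logit p = b0 + b1·A + b2·P + b3·A·P + b4·T + b5·A·P·T

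| Cell | Slope |
|---|---|
| Control, baseline | b4 |
| Intervention arm, baseline | b4 |
| Control, intervention period | b4 |
| Intervention arm, intervention period | b4 + b5 |

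So b5 compares the intervention arm's later slope with a slope pooled over the other three cells.

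**2. Share of a common slope change that enters b5.** In the linear approximation each cell is weighted by its time sum of squares, S(n) = n(n² − 1)/12.

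- S(12) = 12 × 143/12 = 143
- S(18) = 18 × 323/12 = 484.5
- Share = 2 × 143 / (2 × 143 + 484.5) = 286/770.5 = 0.37

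**3. Illustration on assumed figures.** Logistic fits to expected proportions, both arms at 25% in baseline. The change enters with weight min(m, 12)/12 in intervention month m.

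| Scenario | b5, listed terms | b5, period by time added |
|---|---|---|
| No effect, both arms fall to 24% | -0.0012 | 0 |
| No effect, both arms fall to 22% | -0.0038 | 0 |
| No effect, both arms fall to 20% | -0.0069 | 0 |
| True 4.5-point effect, no shared change | -0.0155 | -0.0155 |
| True 4.5-point effect, shared rise of 3 points | -0.0105 | -0.0137 |

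The three shared-fall rows are the same whether time runs on, has a 6-month gap, or restarts at the intervention. For scale, 0.0038/0.0155 = 0.25, and exp(18 × -0.0038) = 0.93 as an 18-month odds ratio.

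**4. When the leak is absent.**

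- With time coded 0 throughout baseline, P·T is the same column as T. The listed set is then complete and b5 = 0 for all three falls.
- With an immediate shared step to 24%, 22% or 20%, b5 = 0, because the period main effect absorbs it.

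**5. Adding intervention by time alone.** With time running through baseline and no period by time, b5 becomes the intervention arm's own before-after slope change: -0.0100 in the 22% case. No section specifies this model, but it is one way of reconciling Sections 10.1 and 10.5.

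**The case against.** The strongest reply is that the list may not be exhaustive, or that time is meant to count from the start of the intervention and be zero before it. Under that coding the stated interpretation holds exactly. Software that adds lower-order terms by itself would also remove the problem. This stands as far as it goes: the defect depends on an unstated coding and is not proof that a wrong model was fitted. But Section 10.5 names one two-way interaction and omits the others, outcomes are measured monthly through baseline, and a primary test should not rest on a software default.

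The second reply concerns size, and it stands. The documents give no shared slope change, so the real bias may be nil. The ramp suits PSA, where a result counts if it falls anywhere in the window. DM depends on the latest A1C and on the medication list at the end of the period, so a shared shift could appear at once and leave b5 untouched. UA/UC counts only the first testing episode in the window, so its ramp need not be linear.

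A reader might also infer a larger leak from the schedule in Section 7.1, headed "Historical practice: Baseline overuse (Month - 17 to Month 0"), which spans 18 months. The Précis and Sections 5.2, 7.2.3 and 10.1 all fix the baseline at 12 months. With Month 1 as September 2020, Month -17 is March 2019, so the span equals March 2019 to February 2020 plus the six excluded pandemic months. The documents do not support an 18-month analysed baseline.

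**Conclusion.** The point holds conditionally. With the terms as listed, 0/1 indicators and time running through the 12 baseline months, the three-way coefficient is not the contrast that Section 10.5 assigns to it. It carries about 37% of any slope change common to both arms (equal weights). That follows from the algebra and is secure. The practical size is not: -0.0038 per month, about a quarter of the figure for a 4.5-point effect, rests on an assumed shared fall of 3 points entering through a 12-month look-back.

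A reader might infer that all three co-primary results are biased by this amount, or that the false-positive rate is inflated by a known factor. The documents support neither. The illustration does not carry over automatically to DM or UA/UC. An error rate would need the shared slope change, the effective sample size and the correlation between overlapping windows, and the documents do not give all of these. The point should be fixed because it concerns the declared primary test and is cheap to repair.

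**What to change.** In Section 10.5, state how time is coded.

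- If time runs through baseline, add period by time to the fixed effects. With 0/1 indicators and a common baseline slope, the three-way coefficient is then the concurrent between-arm slope difference. It is zero when both arms share the same trend change on the log-odds scale.
- If time is zero throughout baseline, say so. The extra term is then redundant, and the model assumes a flat baseline.

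Reconcile Section 10.1's assignment-by-time interactions with the list in 10.5, and do not add intervention by time without period by time.

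The cost is one model term, one or two sentences, and some precision. The standard error of the three-way coefficient rises about 1.11-fold under independent months with equal weights. A rough check on arm-level monthly means with overlapping 12-month windows gives 1.12. Neither figure comes from the planned mixed model, so the loss there is not established.
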